6.3 SCHEMATIC OF STUDY DESIGN

	Pre-ablation	Pre-discharge	3 months
12 lead ECG		X (routine)	X (routine)
Telemetry	X (routine)		
Contrast CT scan or non-contrast CMR for roadmap	X (routine)		
TTE		x (routine)	
Symptom questionnaire	X (research)		X (research)
Clinic Visit			X (EP OPC)
ECG Holter (Mortara)	X (research)		X (research)

**VIVO™ non-invasive Time Assessment
Protocol**

(Vivo protocol)

7. ELIGIBILITY CRITERIA

7.1 INCLUSION CRITERIA

- Subjects who are scheduled for PVC/VT ablation procedure, without structural heart disease
- Age >18 years old and ≤ 80 years
- Fulfil established clinical criteria for catheter ablation of PVC/VT
- Subjects who are at least 18 years or older
- Subjects who have signed an approved Informed Consent Form and applicable subject privacy protection authorization
- Subjects will be selected without regard to gender or age

7.2 EXCLUSION CRITERIA

- Reversible cause of PVC/VT
- Recent cardiovascular event including TIA
- Structural heart disease
- Intolerance or unwillingness to oral anticoagulation with Warfarin
- Bleeding disorder
- Contraindication to CT scan
- Presence of intracardiac thrombus
- Vascular disorder preventing access to femoral veins
- Severe, life threatening non-cardiac disease
- Active malignant disease and recent (<5 years) malignant disease
- Unable or unwilling to comply with F/U requirements
- Renal impairment
- Pregnancy

7.3 DISCONTINUATION/WITHDRAWAL OF PARTICIPANTS AND STOPPING RULES

There are no major additional hazards related to the use of Vivo mapping system to guide the ablation, and the rest of the procedure is carried on using an established ablation strategy. The only difference is in the pre-procedural phase, when Vivo software will be used to localise the ablation targets. Therefore, we do not expect that patients will develop major

side effects related to the intervention tested in this study to warrant withdrawal. However, if patients present with acute medical conditions non-related to the study or new diagnosis are made during the follow-up period, such as active malignant disease, they can be withdrawn from the study. Additionally, patients can be withdrawn on their own request. The patients thus withdrawn from the study will continue to be followed-up regularly in the arrhythmia clinic. There are no major foreseeable circumstances under which the trial will need to be stopped prematurely, other than technical limitations.

8. SUBJECT/PATIENT RECRUITMENT PROCESS

Patient recruitment at a site will only commence once the *study* team has ensured that the following approval/essential documents are in place:

1. HRA approval,
2. Local Site Delegation of Duties and Signature Log is completed (if applicable).

The Royal Brompton Hospital is the single site participating in the trial and will be asked to provide a copy of the following:

1. Signed Clinical *study* Site Agreement (CSSA) (if applicable)
2. Confirmation of capacity and capability

All subjects who wish to enter the study will be fully screened and consented by the Chief Investigator (CI), Principal Investigator or Co-Investigator.

We will recruit patients from those with PVC/VT who have already an indication for catheter ablation according to the current guidelines or have recurrent PVC/VT after previous catheter ablation(s). Patients will be offered participation in the study during the visit in the outpatient clinic. Only one centre will be involved in recruitment of the patients. All electrophysiology consultants in each Trust will be familiar with the protocol and be involved in selection of the patients.

9. STUDY PROCEDURES

9.1 INFORMED CONSENT

Informed consent will be obtained by the Chief Investigator (CI), Principal Investigator (PI) and/or a nominated deputy as recorded on Sponsor's Delegation of Responsibilities Log. Only those members of the study team who have clinical responsibility for the care of

patients under the care of the general medical service will be permitted to undertake informed consent.

Due to the complexity and novelty of the Vivo study, a senior nurse or an SHO cannot take consent for this study. All individuals taking informed consent will have received consent training. Patients will be provided with the information necessary to consider their participation at least 24 hours before the procedure.

Periods shorter than 24 hours will be permitted if the patient feels that further deliberation will not lead to a change in their decision, and provided the person seeking consent is satisfied that the patient has fully retained, understood and deliberated on the information given. Likewise, periods longer than 24 hours will be permitted should the patient request this. The Investigator or designee will explain that the patients are under no obligation to enter the trial and that they can withdraw at any time during the trial, without having to give a reason.

A copy of the signed Informed Consent Form (ICF) along with a copy of the most recent approved Patient Information Sheet (PIS) will be given to the study participant. The original signed consent form will be retained at the study site (one filed in the medical notes and one field in the Trial Master File (TMF)). A copy of the consent form will also be given to the patient.

If new safety information results in significant changes to the risk–benefit assessment, the consent form will be reviewed and updated if necessary. All subjects, including those already being treated, will be informed of the new information, given a copy of the revised consent form and asked to re-consent if they choose to continue in the study.

9.2 RANDOMISATION PROCEDURE

This section does not apply.

9.3 EMERGENCY UN-BLINDING

This section does not apply.

10. STUDY ASSESSMENTS

10.1 SCREENING ASSESSMENTS

Screening

Fifteen patients with PVC/VT and an indication for catheter ablation will be prospectively recruited. The screening visit will involve the following:

- Inclusion and exclusion criteria assessment
- Detailed past medical history including first diagnosis of PVC/VT and related symptoms
- Details of any previous catheter ablation for PVC/VT
- Physical examination
- ECG
- Evaluation of PVC/VT related symptoms
- Standard echocardiography (new or up to 12 months before the procedure)
 - LVEF, LV/RV volumes, LVOT obstruction

10.2 BASELINE ASSESSMENTS

- Detailed past medical history including first diagnosis of PVC/VT and related symptoms
- Physical examination
- ECG
- Evaluation of PVC/VT related symptoms
- Standard laboratory tests
 - complete blood count
 - coagulation studies
 - serum creatinine and electrolytes
 - liver function tests
 - CRP

10.3 TREATMENT PROCEDURE

Using the roadmap 3D image information of the CMR or CT scan a standard three-dimensional (3D) reconstruction will be performed (CARTO software package). The CMR or CT scan will be also imported into the Vivo anatomy software to reconstruct the patient's model, necessary for the following localization analysis.

Before the start of the ablation procedure, when still in the ward, the patient will undergo a 12-lead ECG recording (Mortara) while contemporarily on telemetry in order to record the templates of the different PVC/VT morphologies, with also regards to their frequency. Should the patient present no ventricular arrhythmia, a challenge with exercise bike or

intravenous administration of isoprenaline or atropine could be chosen. Finally, a picture of the patient's chest will be taken and imported in the software to match the ECG electrodes' position.

Mapping Vivo non-contact system and ablation procedure

Once the different templates are acquired, they will be imported into the VIVO analysis system, and a final model with foci localization will be generated. The information will be integrated into the 3D mapping system prior to starting the procedure.

After venous vascular access has been gained using an ultrasound-guided approach, an octapolar catheter (Inquiry™, Saint Jude Medical) will be positioned in His-RV position, while a mapping/ablative catheter will be used both for mapping and RF delivery. In case of arrhythmias originating from the LV, it is the operator's choice to use either an arterial femoral access for a retrograde approach or a transseptal access route. In case of left-sided access, as per institutional standard, ACT measurements will be carried out every 30 min with bolus injections of Heparin to achieve an ACT of ≥ 350 sec.

The whole ablative procedure will be carried out according to international guidelines and as for operator expertise and discretion. Achievement of PVC/VT suppression will be documented for all patients for 30 minutes after last RF delivery, with or without IV drug provocation challenge. DCCV may be carried out at the discretion of the operator during the procedure if needed.

Removal of sheaths will be performed as per institutional standard (+/- protamine).

10.4 SUBSEQUENT ASSESSMENTS

Follow-up

3 months (follow-up visit – study completion - endpoints assessment)

The next scheduled follow-up visit after discharge will be at approximately three months post PVC/VT ablation. The following assessments will take place:

- Patient's symptoms (questionnaire) and clinical assessment
- Review of medication
- 12-lead ECG
- 12-lead Holter (Mortara)
- If high PVC/ VT burden at 3 months, either therapy change or repeat ablation (according to patient and physician preference).

10.5 SUMMARY CHART OF STUDY ASSESSMENTS

	Pre-ablation	Pre-discharge	3 months
12 lead ECG		X (routine)	X (routine)
Telemetry	X (routine)		
Contrast CT scan or non-contrast CMR for roadmap	X (routine)		
TTE		x (routine)	
Symptom questionnaire	X (research)		X (research)
Clinic Visit			X (EP OPC)
ECG Holter (Mortara)	X (research)		X (research)

Follow up

3 months
Follow-up visit

RHYTHM & SAFETY
Review therapy, allow Re-ablation if necessary using same methodology
Assess recurrences by 12-lead Mortara Holter

11. METHODS

11.1 Laboratory Procedures

We will not take specific blood or tissue samples. Routine bloods will be taken at admission for the ablation and pre-discharge.

11.2 Radiology or any other procedure(s)

All patients will undergo a cardiac CMR or CT exam to be used as a roadmap during the ablation procedure. The CT exam will comprise of a standard-of-care contrast-enhanced scan to visualise the cardiac chambers. This pre-procedure imaging is necessary in order to define the spatial anatomical relationship of the cardiac chambers. In the event that the ablation procedure needs to be repeated during follow-up, the roadmap scans can be re-used.

As part of a conventional PVC/VT ablation procedure, the patient is exposed typically to about 2 mSv of ionizing radiation, occasionally increasing to 10 mSv or more, per procedure. If radiation is necessary to be used during any of the study procedures than efforts will be made to lower the exposure to as low as reasonably achievable including the re-use of the CT or CMR scan for 3D image integration during the ablation procedure(s).

- ***Techniques and Interventions***

The technique of mapping the ventricular chambers/epicardial space in order to guide the PVC/VT ablation is a conventional procedure which is carried out routinely in the catheter labs using different mapping system according to operators' experience and confidence. The here proposed study will use the Vivo™ (Catheter Precision, Inc., USA) in the pre-invasive phase in order to guide ablation.

- ***Tools***

All tools used for the ablation procedure will include standard materials for ablation of PVC/VT. The Vivo™ Anatomy and Analysis software and the Kinect Camera are fully CE marked.

- ***Study Drugs***

This section does not apply.

11.3 DEFINITION OF THE END OF STUDY

The end of trial will be considered the last patient last visit (hospital visit).

12. SAFETY REPORTING

12.1 DEFINITIONS

Adverse Event (AE) — any untoward medical occurrence in a patient or clinical study subject who is administered a treatment and which does not necessarily have a causal relationship with this treatment (*i.e.* any unfavourable or unintended change in the structure (signs), function (symptoms), or chemistry (lab data) in a subject to whom a treatment/study procedure has been administered, including occurrences unrelated to that product/procedure/device).

Serious Adverse Event (SAE) – is defined as an untoward occurrence that:

- Results in death; or
- Is life-threatening (places the subject, in the view of the Investigator, at immediate risk of death)
- Requires hospitalization or prolongation of existing hospitalization (hospitalisation is defined as an inpatient admission, regardless of length of stay; even if it is a precautionary measure for observation; including hospitalisation for an elective procedure, for a pre-existing condition)
- Results in persistent or significant disability or incapacity (substantial disruption of one's ability to conduct normal life functions)
- Consists of a congenital anomaly or birth defect (in offspring of subjects or their parents taking the study drug regardless of time of diagnosis)
- Is otherwise considered medically significant by the investigator.

Important medical events that may not be immediately life-threatening or result in death or hospitalisation but may jeopardise the subject or may require intervention to prevent one of the outcomes listed in the definition of serious will also be considered serious.

12.2 RECORDING ADVERSE EVENTS (AEs)

All Adverse Events will be recorded in the hospital notes and Case Report Form (CRF). If the Investigator suspects that the disease has progressed faster due to the administration of the study treatment/procedure, then he/she will report this as an unexpected adverse event to the Sponsor and the REC as detailed in Section 12.3.

12.2 ASSESSMENT OF SAEs

Principal Investigator (PI) at all sites must report all SAEs to the Chief Investigator (CI) or a delegated individual in the research team. The CI and his research team at RBH are responsible for reporting events to the Research Office immediately and/or within 24 hours of becoming aware of the event using the Sponsor's SAE Reporting Form.

Classification and causality of Adverse Events (AEs) will be conducted by local PIs and reviewed by CI. The CI cannot downgrade the site PI's classification and if there is disagreement which cannot be resolved during formal discussion then the assessment of the site PI will be accepted. The CI, can however, upgrade the seriousness of an event without consultation with the site PI.

12.3 REPORTING OF SAEs TO THE SPONSOR AND THE REC

All AEs that are to be reported to the Research Office must be recorded, signed and dated by the Investigator at site. Research Office accepts study specific SAE forms, HRA SAE Form or RB&HFT template SAE Reporting Form available [here](#).

Information can be submitted in electronic format:

- E-mail: [contact]
- [contact].

An SAE occurring to a research participant will be reported to the Research Ethics Committee (REC) that gave a favorable opinion of the study (the 'main REC'), the study Sponsor (RB&HFT Research Office) and the local R&D Office where in the opinion of the CI/PI the event was:

- '**related**': that is, it resulted from administration of any of the research procedures; and
- '**Unexpected**': that is, the type of event is not listed in the protocol as an expected occurrence.

Reports of related and unexpected SAEs will be submitted within 15 days of the CI/PI becoming aware of the event; using the SAE reporting form for non-CTIMPs published [on the HRA website and entitled non-CTIMP safety report to REC](#). The form should be completed in typescript and signed by the Chief Investigator (CI) prior to submission to the REC.

Reports of SAEs in double-blind studies should be un-blinded.

The coordinator of the main REC will acknowledge receipt of safety reports within 30 days. It is the responsibility of the CI and his/her research team to send a copy of the SAE notification and acknowledgement receipt to the Research Office.

The research team also has the responsibility to report SAEs occurring in a certain period (28 days) after a patient completes the study. Any SAEs reported to the Investigators during this phase must be documented in the patient's medical notes and submitted via an SAE form

12.4 THE TYPE AND DURATION OF THE FOLLOW-UP OF SUBJECTS AFTER AEs

The type and duration of follow-up care for subjects following an SAE will be as follows: 6-12 months following phrenic nerve palsy, valve damage; 3-6 months following vascular complications or pericardial effusion (usually these complications are promptly treated without major long-term consequence).

12.5 PREGNANCY

Pregnant patients will be excluded from the study. However, if pregnancy occurs after inclusion into the study, we will record and notify pregnancies occurring during the study period to the Sponsor.

Follow-up of pregnant subject:

- No further ablation procedure will be undertaken during the pregnancy period in order to avoid radiation exposure and hazards to the foetus.
- Medication contraindicated during pregnancy will be withdrawn.
- No additional investigations involving radiation exposure such as CT, X ray will be performed, unless clinically urgent.

Follow-up of child born to a pregnant trial subject, including male trial subject who is the partner of the pregnant woman:

Children born to a pregnant subject are unlikely to be affected by the participation of the parent in the study. For safety reasons, a specialised paediatric team will follow children for 1 year.

12.6 ANNUAL PROGRESS REPORTS (APRs)

The Chief Investigator will prepare the APR for the study. It will be reviewed by the RO and sent to the REC by the CI within 30 days of the anniversary date on which the favourable opinion was given by the REC, and annually until the study is declared ended.

12.7 REPORTING URGENT SAFETY MEASURES

The Sponsor and/or the Investigator may take appropriate urgent safety measures in order to protect the subjects of a clinical study against any immediate hazard to their health or safety. If safety measures are taken, REC approval is not required before the measure is taken.

The Investigator will immediately and in any event no later than 3 days from the date the measures are taken, give written notice to the REC and the study Sponsor of the measures taken and the circumstances giving rise to those measures.

In order to prevent any delays in the reporting timelines the Sponsor has delegated this responsibility to the CI/PI. Therefore the CI/PI must report any urgent safety measures to the REC directly, and in parallel to the Sponsor. The REC coordinator will acknowledge receipt of urgent safety measures within 30 days.

13. DATA MANAGEMENT AND QUALITY ASSURANCE

13.1 CONFIDENTIALITY

All data will be handled in accordance with the Data Protection Act 1998, NHS Caldecott Principles, The Research Governance Framework for Health and Social Care, 2nd Edition (2005), and the condition of the REC approval.

The Case Report Forms (CRFs) will not bear the subject's name or other personal identifiable data. The subject's initials, Date of Birth (DOB) and study Identification Number (ID), will be used for identification.

13.2 DATA COLLECTION TOOL

Case Report Forms (CRF) will be designed by the CI and the final version will be reviewed and discussed with the study Sponsor. All data will be entered legibly in black ink with a ball-point pen. If the Investigator makes an error, it will be crossed through with a single line in such a way to ensure that the original entry can still be read. The correct entry will then be clearly inserted. The amendment will be initialled and dated by the person making the correction immediately. Overwriting or use of correction fluid will not be permitted.

It is the Investigator's responsibility to ensure the accuracy of all data entered and recorded in the CRFs. The Delegation of Responsibilities Log will identify all study personnel responsible for data collection, entry, handling and managing the database.

Data will be firstly recorded into source documents (i.e medical notes) (medical history, baseline investigations) and then recorded onto the CRF (with the addition of the procedure specific data).

Methods used to maximise completeness of data will include telephoning subjects who have not attended the planned follow-up visit.

13.3 DATA HANDLING AND ANALYSIS

- Excel software will be used for data entry.
- In order to ensure validity and quality of data we will use cross validation
- Data will be stored and backed up on 2 additional hard drives on two different sites in order to allow recovery of data in case of a disaster such as fire/flooding/ theft. The PI and their collaborators/co-workers will be responsible for data entry and quality of data collection. Analysis will be performed by the study investigators and reviewed independently of data entry by the statistical team.
- Every patient will receive a numerical patient identifier and all data that is transferred outside the primary hospital will exclusively be identified by this study number.
- The study database will be held at a server at the Royal Brompton Hospital.

13.4 ARCHIVING ARRANGEMENTS

The study documents (including the Study Master File (SMF), Case Report Forms (CRFs), Informed Consent Forms along with the study database) will be kept for a minimum of five years. They will be stored in locked offices within the Royal Brompton and Harefield NHS Foundation Trust (RB&HFT). The CI is responsible for the secure archiving of study documents. The study database will also be kept electronically on the RB&HFT computer network, for a minimum of five years.

The approved repository for longer retention of local materials for studies that involve RB&HFT patients is Box-It Storage UK. The study documentation will be prepared for archiving by the research team in line with the Research Office Archiving SOP and the transfer will be arranged by the Research Office.

Patient anonymised data may be exported for the purpose of offline review and to perform the image merge as part of the study and also to further develop the technology.

14. STATISTICAL DESIGN

This is a prospective, non-randomised, observational study which will recruit 15 non-selected patients with PVC/VT eligible for catheter ablation, without structural heart disease.

Procedural outcomes will be compared to age & gender matched procedures of the same operator from the last 5 years' database.

The statistical design was decided in collaboration with the study PIs and will be descriptive only.

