4.3 STUDY RATIONALE AND RISK/BENEFIT ANALYSIS

4.3.1 Mapping PVC/VT

Outflow tract ventricular tachycardia or frequent premature ventricular tachycardia (PVCs) often occur in the absence of structural heart disease and account for 10% of all ventricular tachycardia (VT). The majority of these originate from the right ventricular outflow tract and the remainder from the left ventricular outflow tract, including cusps of the aortic valve 10. Eighty to 90% of tachycardia in normal hearts originate from the right ventricle, most commonly the right ventricular outflow tract (RVOT)¹¹.

Especially in ischaemic patients, but not only, scar-related re-entry ventricular arrhythmia may involve the endocardium, mid-myocardium, and epicardium. Importantly, the presence of epicardial VT circuits (in about 32% of patients with post-myocardial infarction scars) is considered one of the reasons for failure of a subset of endocardial ablations. Consequently, epicardial mapping via subxyphoidal puncture has evolved as an essential procedure for mapping epicardial scar EP substrate and guiding epicardial ablation, especially in ischaemic cardiomyopathy patients with failed endocardial ablation. Epicardial mapping is associated with procedural complexity and risk of complications. In some cases, catheter access to the epicardium is limited by the presence of pericardial adherence. Non-invasive mapping of epicardial EP substrate and VT activation is therefore a highly desirable procedure. It could aid in deciding whether endocardial or epicardial approach should be used and provide important information for the pre-procedural planning of epicardial ablation. With regards to

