5. STUDY OBJECTIVES

5.1 PRIMARY OBJECTIVE

Our hypothesis is that patients with PVCs/VT who must undergo catheter ablation can benefit from a VIVO non-contact mapping and guided ablation in terms of efficacy to decrease the procedural time of the ablation and acute success.

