6. STUDY DESIGN

6.1 OVERALL DESIGN

This is a prospective, single arm, observational and feasibility study, which will recruit 15 non-selected patients, with structurally normal heart, with a conventional indication for catheter ablation of PVCs/VT. The follow up will be of three months. The study will also include another retrospective cohort, including age & gender matched patients, without cardiac structural disease, with a conventional indication for catheter ablation of PVCs/VT from the last 5 years' database of the same operator. For this second retrospective cohort there will be no follow-up.

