14.1 SAMPLE SIZE AND RECRUITMENT

This is a feasibility pilot study, which will test the feasibility of PVC/VT foci mapping with Vivo system and catheter ablation in unselected patients without structural heart disease, eligible for PVC/VT ablation. Therefore, no power calculation has been done and the number of patient recruited will be of 15 which are deemed sufficient by the CI and Co-PIs on a clinical basis.

The estimated recruitment period for the trial will be of 6 months. We estimate that this sample size is attainable in practice, as the number of PVC/VT ablation procedures per year performed within the Trust is around 100. We also included patients with previous PVC/VT ablation in order to maximise chances of recruitment. This pilot is performed with the intention to plan a prospective multi-operator/multicentre trial which is adequately powered. We will aim to compare the procedure parameters as well as the outcome of this trial to age & gender matched procedures of the same operators from the last 5 years' database.

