14.2 ENDPOINTS

14.2.1 Primary endpoints

Safety:

- Absence of acute adverse events due to the use of VIVO system during PVC/VT ablation
- Safety endpoint of the entire mapping and ablation strategy

Efficacy:

- To assess the efficacy of VIVO to decrease procedure time as compared to standard of care ablation procedures.

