14.3 STATISTICAL ANALYSIS PLAN

Descriptive statistic data with regard to baseline and procedural variables will be reported; continuous variables will be expressed by mean \pm standard deviation or median and interquartile range (25th, 75th percentile), depending on the normality of distribution; categorical variables will be summarized by frequencies and percentages. The outcome of radiofrequency ablation on the entire cohort of patients will be presented in the form of percentage of patients free from symptomatic or documented arrhythmia or with only mild symptoms related to arrhythmia recurrence.

Depending on the severity of symptoms and documentation of tachycardia during follow-up, patients will be divided into two groups (success/recurrence). Baseline characteristics and procedural variables will be compared between these two groups by student t-tests, Mann Whitney U tests, or Fisher's exact test where appropriate in order to identify those variables associated with better mid/long term outcomes. A two-tailed p value <0.05 will be considered statistically significant. Intra-patient improvement from baseline to 6 months follow-up visit will be assessed by McNemar's test. Freedom from PVC/VT will be assessed as a time-dependent variable using Cox proportional hazard models.

To judge if ablation strategy using Vivo mapping system is as successful in achieving the clinical endpoint, we will compare the procedure parameters as well as the outcome of this trial to age & gender matched procedures of the same operator from the last 5 years' database.

To measure the strength of association between the acute successes (PVC/VT suppression at the end of the ablation) and outcome, a McNemar test will be performed. Data will be analyzed using SPSS version 18 (IBM Corporation).

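### The historical controls for procedure time are matched only on age and gender, so chamber of origin and first versus repeat ablation are uncontrolled; Section 4.3.2b also needs reconciling with 10.3 and 11.2 on when VIVO output is used (minor)

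*Combined protocol and SAP*

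**What the plan says.** The primary efficacy endpoint in Section 14.2.1 is: "To assess the efficacy of VIVO to decrease procedure time as compared to standard of care ablation procedures". Section 5.1 adds acute success to the hypothesis: "in terms of efficacy to decrease the procedural time of the ablation and acute success".

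The comparator is retrospective. Section 6.1 describes it as "another retrospective cohort, including age & gender matched patients, without cardiac structural disease" and requires a conventional ablation indication. Section 14 gives the matching rule: "Procedural outcomes will be compared to age & gender matched procedures of the same operator from the last 5" years. Section 14.3 repeats the matching rule: "age & gender matched procedures of the same operator from the last 5" years. Section 14.1 uses the same rule but writes of operators in the plural. The Synopsis says the controls are matched without naming the variables. No section gives the number of controls or a matching ratio, and Section 14.6 lists no further statistical considerations.

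The protocol itself shows that cases differ in two ways that could affect duration.

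- **Chamber of origin.** Section 4.3.1 states: "Eighty to 90% of tachycardia in normal hearts originate from the right ventricle". Section 4.3.2c asks for different anatomical maps in left-sided and right-sided cases. Section 10.3 gives left-ventricular cases an arterial or transseptal route and adds ACT checks every 30 min when access is left-sided.
- **First versus repeat ablation.** Section 14.1 says: "We also included patients with previous PVC/VT ablation in order to maximise chances of recruitment". Section 8 also admits patients with recurrence after earlier ablation.

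Both factors are captured for VIVO patients: previous ablation at screening (10.1) and the site of origin tagged in CARTO (4.3.2d).

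On the use of VIVO output, Section 4.3.2b allows it to be integrated into mapping or, alternatively, used in post-processing to check accuracy. Section 10.3 has it integrated before the procedure starts. Section 11.2 has it used before the invasive phase to guide ablation.

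**The concern.** Age and gender are the only patient-level matching variables. If the VIVO cohort and the controls differ in the share of non-RV cases or of repeat ablations, and these cases take a different time, the crude time difference mixes the VIVO effect with case mix. It could show a saving that is not there or hide one that is. The documents fix neither the direction nor the size.

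The pilot is meant to lead to an adequately powered trial (14.1), and Section 14.3 uses the same controls to judge whether the VIVO strategy is as successful. A time difference that cannot be separated from case mix is weak input for either purpose.

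The wording of 4.3.2b matters for the same endpoint. A procedure run without VIVO output beforehand cannot be shortened by it, and the plan does not say how such a case would be counted.

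**Working it through.** **Plan's own figure.** The sample size of 15 is set on clinical grounds without a power calculation (14.1), so there is nothing to reproduce.

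**Inputs from the documents.** 15 VIVO patients (14.1); 80 to 90% RV origin in normal hearts (4.3.1), hence 10 to 20% other.

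**Assumed inputs** (the documents give none of these). SD of procedure time 30 to 75 min; extra time per harder case 20 to 60 min; difference between cohorts in the share of harder cases 5 to 30 points; 15 controls, with 60 as an alternative.

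**1. Case-mix bias** = difference in share × extra minutes.
- One factor, smallest: 0.05 × 20 = 1 min. Middle: 0.20 × 30 = 6 min. Largest: 0.30 × 60 = 18 min.
- Two factors acting in the same direction, largest: 2 × 0.30 × 60 = 36 min.

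**2. Random error.** SE = SD × √(1/15 + 1/n_control); half-width = t × SE, with t = 2.048 on 28 df at 15 v 15.

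| SD (min) | SE, 15 v 15 | 95% half-width, 15 v 15 | 95% half-width, 15 v 60 |
|---|---|---|---|
| 30 | 11.0 | 22.4 | 17.3 |
| 45 | 16.4 | 33.7 | 25.9 |
| 60 | 21.9 | 44.9 | 34.5 |
| 75 | 27.4 | 56.1 | 43.1 |

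**3. Comparison.** At 15 v 15 one factor (at most 18 min) stays below the half-width (at least 22.4 min). Two factors need not: at 20 points and 60 min each the bias is 2 × 0.20 × 60 = 24 min, against 22.4 min at SD 30. Extra controls shrink the half-width but not the bias: 18 min exceeds 17.3 min at SD 30 with 60 controls. A 12-min bias lowers the coverage of a nominal 95% interval at 15 v 15 to 80.5% (SD 30) or 88.7% (SD 45).

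**4. Chance imbalance.** With the same expected non-RV share in both cohorts (10 to 20%), the probability that 15 v 15 differ by 3 or more non-RV patients (20 points) is 0.12 to 0.25.

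**5. Does adjusting for chamber improve precision?** Simulation at 15 v 15, 85% RV in both cohorts, SD now within chamber, mean 95% half-width:
- gap 60, SD 45: 36.9 min unadjusted, 34.0 adjusted (1 − 34.0/36.9 = 8% narrower);
- gap 30, SD 60: 45.3 and 45.4, no gain.

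The gain appears only when the chamber gap is large relative to the SD.

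**6. How much adjustment is affordable?** Expected non-RV cases among 15: 15 × 0.10 = 1.5 to 15 × 0.20 = 3. The chance of none is 0.9^15 = 0.21 to 0.8^15 = 0.035. One or two terms is the limit.

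**7. Unguided cases.** If a fraction f has VIVO output only in post-processing, an assumed 30-min saving becomes 30 × (1 − f): 24 min at f = 0.20 and 15 min at f = 0.50. One case in 15 costs 30/15 = 2 min. Leaving such cases out has its own risk: dropping one of 15 that runs 60 min longer than the rest creates a spurious saving of 60/15 = 4 min (2 min at 30, 6 min at 90).

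**The case against.** The study is a 15-patient feasibility pilot, described in Section 14 as descriptive only and intended to precede a powered trial. The controls are not arbitrary: operator, time window, cardiac structure and indication are all restricted. Section 14.3 already commits to reporting baseline and procedural variables, and both case-mix factors are collected for VIVO patients. With so few non-RV cases, matching on chamber may prove impracticable. The final ablation site is found after VIVO-guided mapping in one cohort only, so it may be ascertained differently in the two. All of this stands. It limits the severity and narrows the gap to this: nothing says the factors will be tabulated for the controls or used in the comparison.

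Three stronger readings are tempting but not supported.

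- A reader might infer that the bias is only a few minutes and below random error. The documents supply no figure for this, and step 3 shows plausible settings where it fails. They equally do not show that the bias is large.
- A reader might infer that adjusting for chamber always narrows the interval, or that the plan fixes one control per case. Step 5 contradicts the first, and no section states a ratio.
- A reader might infer that 4.3.2b also contradicts 4.3.2d. It does not: 4.3.2d fixes when localisation is done, not when its result is used. Even against 10.3 and 11.2, 4.3.2b may refer only to the accuracy check in 4.3.2e, and 10.3 provides a provocation challenge when no arrhythmia is seen. The wording still leaves the matter open.

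**Conclusion.** The point holds as a minor weakness that is cheap to repair. The comparison behind the sole efficacy endpoint of 14.2.1 leaves chamber of origin and first versus repeat ablation uncontrolled, and case mix could move the time difference either way. The size cannot be derived from the documents. The ranges of 1 to 18 min for one factor and up to 36 min for two, against a half-width of 22 to 56 min at 15 v 15, rest entirely on the assumed SDs, time gaps, share differences and control number. The main reason to control for case mix is bias; better precision is a conditional extra. Section 4.3.2b is at odds with 10.3 and 11.2 as written, and these sections must be reconciled.

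**What to change.** **(a) Sections 6.1, 14 and 14.3.**
- Draw controls from all consecutive eligible procedures of the same operator in the 5-year window, with more than one per case where available, and state the ratio.
- In addition to age and gender, match on or adjust for first versus repeat ablation and chamber (RV versus other), limited to one or two terms.
- Define chamber in both cohorts by the final mapping or ablation site, and flag the best-guess sites that 4.3.2d allows.
- If too few non-RV cases occur, tabulate both factors in both cohorts instead.
- Report the time difference with a 95% CI and without attributing it causally to VIVO.

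**(b) Sections 4.3.2b, 10.3 and 11.2.**
- Reconcile the three sections.
- Record for each case whether VIVO output was available before mapping.
- Keep every VIVO case in the main comparison and show guided cases alone as secondary.

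**Cost.** Changes of wording, one CRF item, and abstraction of chamber and previous ablation for the controls. The documents do not list the database fields, so some chart review may be needed. No more prospective patients are required. Only about 1.5 to 3 non-RV VIVO cases are expected, the number of eligible controls is unknown, the site may be ascertained differently in the two cohorts, and residual confounding will remain.
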